9.4. Concomitant and Other Medications

At Visit 1 subjects will be questioned about current concomitant medication use. At Visit 2, Visit 3 and Visit 4 subjects will be questioned about ongoing or new concomitant medication use.

Concomitant medications are defined as medications either ongoing or ended on or after the first dose of study medication. All concomitant medications taken since screening until the end of the study will be listed by treatment and subject. If the end date and 'ongoing' are missing, then the medication will be considered as concomitant medication. Medication taken after last randomized treatment will be identified and flagged in the listing.

9.4.1. Missing and Partial Concomitant and Other Medication Start and Stop Dates

For the purpose of inclusion in prior and/or concomitant medication tables, incomplete medication start and stop dates will be imputed as follows:

- If year and month are present and day is missing, then set day to first day of month for start date, and set day to last day of month for end date
- If year and day are present and month is missing, then set month to January for start date, and set month to December for end date
- If year is present and month and day are missing, then set month and day to January 1 for start date, and set month and day to December 31 for end date
- Completely missing date will not be imputed

The partial dates will be provided as such in the subject data listings (with the imputed dates).

9.5. Pregnancy Test

All females of child bearing potential will have a urine pregnancy test at Visits 1, 2 and final Visit 4.

Pregnancy test results will be listed by treatment and subject.

9.6. Vital Signs

The subject's post-baseline vital signs will be recorded (pulse rates, sitting systolic and diastolic blood pressure) at Visits 3 and 4. Height and weight will also be recorded at Visit 4. Descriptive statistics (number of subjects, mean, standard deviation, median, minimum and maximum) will be used to summarize vital sign results and changes from baseline by treatment group and visit.

Values outside the respective normal range and values deemed as clinically significant by the Investigator will be listed. Normal ranges for pulse rate, systolic BP and diastolic BP are listed in Table 7.

Table 7: Normal ranges of vital signs ^{6,7}

Vital Sign	Abnormal Criteria
Pulse Rate (Beats/min)	Pulse rate: 6-11 years and Result is <60 or >95
Systolic BP (mmHG)	Systolic BP: 6-9 years and Result is <95 or >110 Systolic BP: 10-11 years and Result is <100 or >119
Diastolic BP(mmHG)	Diastolic BP: 6-9 years and Result is <60 or >73 Diastolic BP: 10-11 years and Result is <65 or >76

The number of subjects with values of potential clinical significance determined by the investigator will be tabulated by treatment group and visit.

All vital sign data will be listed by treatment and subject.

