13.8.4. Vital Signs

Descriptive statistics will be used to summarize vital sign results and changes from baseline by treatment group and time. Values of potential clinical significance will be defined in the SAP. The number of subjects with values of potential clinical significance will be tabulated. All vital signs data will be displayed in listings.

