9. SAFETY AND TOLERABILITY

9.1. Overall Summary of Tolerability

The safety analyses will be based on the SAS, unless otherwise specified. If a subject is randomized in the study more than one time, it will be decided at the Blind Data Review Meeting (BDRM) or after unblinding, on a case by case basis if the subject is counted in the numerator of any specific safety analysis.

Table 6 provides an overview of the planned analyses.

Table 6: Overview of Planned Safety Analyses

Display Type	Data Displays Generated		
	Table	Figure	Listing
Adverse Events			
Overview	Y[2]		
Treatment Emergent AEs	Y[1][2]		Y
Treatment Emergent AEs Severity	Y[2]		Y
Treatment-Related Emergent AEs	Y[2]		Y
Placebo Run-In Period AEs	Y[2]		Y
Pre-run-in period AEs			Y
AEs Leading to Withdrawal			Y
SAEs	Y[2]		Y
Treatment Emergent SAEs	Y[2]		Y
Treatment Emergent SAEs Severity	Y[2]		Y
Treatment-Related Emergent SAEs	Y[2]		
Laboratory			
Pregnancy Test Results			Y
Other			
Vital Signs	Y[3] [2]		Y
Physical Examination	Y[4] [2]		Y
Focused ENT Examination	Y[5] [2]		Y

NOTES :

- Y = Yes display generated.
- [1]: Display will also be produced by SOC, severity, and by relationship to study medication
- [2]: Display will be based on safety analysis set
- [3]: Display will be produced separately for overall summary (inc. change from baseline), for potentially clinically significant results, and shift tables
- [4]: Display will be produced separately for overall summary
- [5]: Display will be produced separately for overall summary and for potentially clinically significant results

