Table 14.3.2.1.2 Summary of Potentially Clinically Significant Vital Signs (Safety Analysis Set)

Parameter: Systolic Blood Pressure (mmHg)

Treatment Group	Visit	n	Number (%) of subjects			
			Normal	Abnormal	Abnormal, NCS	Abnormal, CS
Placebo NS (N=xxx)	Screening	xx	xxx (xx.x)	xxx (xx.x)	xxx (xx.x)	xxx (xx.x)
	Baseline	xx	xxx (xx.x)	xxx (xx.x)	xxx (xx.x)	xxx (xx.x)
	Day 8	xx	xxx (xx.x)	xxx (xx.x)	xxx (xx.x)	xxx (xx.x)
	Day 15/Early Termination	xx	xxx (xx.x)	xxx (xx.x)	xxx (xx.x)	xxx (xx.x)
GSP 301 NS (N=xxx)	Screening	xx	xxx (xx.x)	xxx (xx.x)	xxx (xx.x)	xxx (xx.x)
	Baseline	xx	xxx (xx.x)	xxx (xx.x)	xxx (xx.x)	xxx (xx.x)
	Day 8	xx	xxx (xx.x)	xxx (xx.x)	xxx (xx.x)	xxx (xx.x)
	Day 15/Early Termination	xx	xxx (xx.x)	xxx (xx.x)	xxx (xx.x)	xxx (xx.x)

Source: Listing 16.2.8.5

N= Number of subjects in SAS treatment arm; n= Number of subjects that has test for each visit; percentages are based on n.

Baseline is defined as the value collected at Randomization Visit 2.

CS = Clinically Significant; NCS = Not clinically significant

Program: xxxx.sas Executed: DDMMYY YYYY HH:MM

Page X of Y

Programming Note: Vital Sign parameters Systolic blood pressure (mmHg), diastolic blood pressure (mmHg) and pulse rate (BEATS/MIN) will be displayed.

Table 14.3.2.2.1 Summary of Physical Examination (Safety Analysis Set)

General Appearance

Treatment Group	Visit	n	Number (%) of subjects			
			Normal	Abnormal	Abnormal, NCS	Abnormal, CS
Placebo NS (N=xxx)	Baseline	xx	xxx (xx.x)	xxx (xx.x)	xxx (xx.x)	xxx (xx.x)
	Day 15/Early Termination	xx	xxx (xx.x)	xxx (xx.x)	xxx (xx.x)	xxx (xx.x)
GSP 301 NS (N=xxx)	Baseline	xx	xxx (xx.x)	xxx (xx.x)	xxx (xx.x)	xxx (xx.x)
	Day 15/Early Termination	xx	xxx (xx.x)	xxx (xx.x)	xxx (xx.x)	xxx (xx.x)

Source: Listing 16.2.8.2

N= Number of subjects in SAS treatment arm; n= Number of subjects that has test for each visit; percentages are based on n.

Baseline is defined as the value collected at Screening Visit 1.

CS = Clinically Significant; NCS = Not clinically significant

Program: xxxx.sas Executed: DDMMYY YYYY HH:MM

Page X of Y

Programming Note: Repeat table for all PEs: Neck, head and eyes, cardiovascular system, respiratory system, Musculoskeletal System, Skin, Gastrointestinal System, Genitourinary System, Neurological Examination

Table 14.3.2.3.1 Summary of Focused ENT Examination (Safety Analysis Set)

ENT Examination: Nasal Irritation [a]

Visit	Result	Number (%) of subjects	
		Placebo NS (N=xxx)	GSP 301 NS (N=xxx)

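### The categorical vital-sign table pools low and high values with no link to baseline, and the promised shift table has no shell (minor)

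*SAP*

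**What the plan says.** Vital signs are a named safety endpoint in both documents. SAP section 9.6, Table 7, sets these criteria for an abnormal value:

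- "Systolic BP: 6-9 years and Result is <95 or >110"
- "Systolic BP: 10-11 years and Result is <100 or >119"
- "Diastolic BP: 6-9 years and Result is <60 or >73"
- "Diastolic BP: 10-11 years and Result is <65 or >76"
- "Pulse rate: 6-11 years and Result is <60 or >95"

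Each criterion uses one reading and an age band. None refers to the child's earlier values.

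The section says that out-of-range values are listed, and that the count to be tabulated is the number judged clinically significant by the investigator. Shell Table 14.3.2.1.2 shows, by arm and visit, the columns Normal; Abnormal; Abnormal, NCS; and Abnormal, CS. It has Screening, Baseline, Day 8 and Day 15/Early Termination rows. It has no low or high column, and its notes do not cite Table 7.

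Note [3] to SAP Table 6 (section 9.1) promises more for vital signs: "Display will be produced separately for overall summary (inc. change from baseline), for potentially clinically significant results, and shift tables". The SAP's list of tables and its shells contain only two vital-sign tables: 14.3.2.1.1 (values and change from baseline) and 14.3.2.1.2. Neither is a shift table.

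**The concern.** A categorical safety table should show how many children crossed a limit on treatment, and on which side. A single two-sided count per visit does neither. If blood pressure rises in one arm, some children leave the low side while others enter the high side, and the pooled column shows only the net result. A similar Abnormal percentage in the two arms could then be read as reassurance although the high counts differ. Children already outside the range at baseline are counted again at each later visit, which adds background to the comparison. A shift table would address both problems, but it exists only as a table note.

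**Working it through.** **Inputs.** The limits come from SAP Table 7. The number per arm, 225, comes from SAP section 4.3.1: 382 / (1 − 0.15) = 449.4, about 450 randomized, or 225 per arm. The plan states no expected rate of abnormal vital signs, so there is no figure of its own to reproduce. Neither document gives a blood-pressure mean or SD. The following are therefore assumptions: normal distribution, whole-mmHg readings, and SD 6 to 10 mmHg.

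**Formula.** With lower limit L, upper limit U, mean m and SD s:

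- Low = Φ((L − 0.5 − m)/s)
- High = 1 − Φ((U + 0.5 − m)/s)
- Pooled = Low + High

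**Step 1: offsetting.** Let c be the midpoint of the range. For a distribution symmetric about its mean, moving the mean from c − d to c + d swaps Low and High. Pooled is then unchanged, whatever the SD. Under the normal model, a rise that ends closer to c than it began lowers Pooled.

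For systolic pressure at 6-9 years, L = 95, U = 110 and c = 102.5. At s = 10 and m = 100.5:

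- Low = Φ((94.5 − 100.5)/10) = Φ(−0.6) = 27.4%
- High = 1 − Φ((110.5 − 100.5)/10) = 1 − Φ(1.0) = 15.9%
- Pooled = 43.3%

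At m = 104.5 the two tails swap. Other starting points at SD 10 (sums subject to rounding):

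| Mean (mmHg) | Low | High | Pooled |
|---|---|---|---|
| 100.5 → 104.5 | 27.4% → 15.9% | 15.9% → 27.4% | 43.3% → 43.3% |
| 96.5 → 102.5 | 42.1% → 21.2% | 8.1% → 21.2% | 50.1% → 42.4% |
| 102.5 → 105.5 | 21.2% → 13.6% | 21.2% → 30.9% | 42.4% → 44.4% |
| 104 → 108 | 17.1% → 8.9% | 25.8% → 40.1% | 42.9% → 49.0% |

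If all 225 children per arm fell under the 6-9 year limits (a simplification), the first row is a pooled difference of 0 children, against about 36 versus 62 with high values. The third row is about 5 children pooled against about 22 high. The fourth is about 14 against about 32, so the pooled count does respond when the mean starts above the midpoint, but less than the high count.

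**Step 2: background rate.** For a given SD, the two-sided rate is lowest when the mean sits at the midpoint, where it equals 2 × (1 − Φ((width/2 + 0.5)/s)):

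| Band | Width (mmHg) | SD 6 | SD 8 | SD 10 |
|---|---|---|---|---|
| SBP 6-9 y | 15 | 18% | 32% | 42% |
| SBP 10-11 y | 19 | 10% | 21% | 32% |
| DBP 6-9 y | 13 | 24% | 38% | 48% |
| DBP 10-11 y | 11 | 32% | 45% | 55% |

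The range is thus 10-32% at SD 6 and 21-55% at SD 8-10. Pulse has a range 35 beats/min wide and gives only 2-13% at SD 8-12, so the narrow-range point does not apply to it.

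**Step 3: the missing table.** Table 6 note [3] names shift tables. The list of tables and the shells run from 14.3.2.1.2 straight to the physical examination table. This gap does not depend on any assumption.

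**The case against.** Several points on the other side stand.

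- **The link to Table 7 is inferred.** Section 9.6 says that out-of-range values are listed, and the shell does not cite Table 7. The column appears to use those limits. If it instead came from the site's own assessment, the rates in Step 2 would not apply, but the column would still carry no direction.
- **Other displays help.** Table 14.3.2.1.1 gives change from baseline by arm and visit; in the 4 mmHg illustration at SD 10, a comparison of means would have about 99% power. Baseline rows show the background rate. The CS column reflects investigator judgement. Protocol section 11.1 has clinically significant findings, including worsening from baseline, recorded as adverse events. Listing 16.2.8.5 shows every value. None of these tabulates by arm how many children newly crossed a limit, and in which direction.
- **The display is descriptive.** No test is planned on the column, and the exactly symmetric example is the worst case.
- **Tables can be added later.** SAP section 6.2 allows extra tables after the analysis, but those would be post hoc.

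A reader might also infer that the SAP breaks the protocol's statement in section 13.8.4, "Values of potential clinical significance will be defined in the SAP". The documents do not support making much of this. The SAP assigns significance to the investigator, and protocol section 13 lets the SAP prevail where the two differ.

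**Conclusion.** The point holds as a minor improvement to a descriptive safety display. Three facts rest on the documents alone: the abnormal criteria are two-sided, the shell has one undirected column with no within-child link to baseline, and the promised shift tables are missing. The offsetting follows by arithmetic for any symmetric distribution; how much is lost depends on where the mean lies.

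Two stronger readings are tempting and not supported. One is that about a third to a half of untreated children would be flagged. The documents give no mean or SD; the rate is 10-32% per blood-pressure parameter and band at SD 6, and systolic pressure at 10-11 years stays below a third up to SD 10 when centred. The other is that the plan could not detect a blood-pressure effect. That limitation concerns the pooled column only, since mean change by arm would show an average rise. Nothing here suggests that the drug raises blood pressure, and the Table 7 limits themselves are not in question.

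**What to change.** Leave the Table 7 limits as they are and make three changes to the SAP:

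1. In Table 14.3.2.1.2, replace Abnormal with Low and High, each keeping its NCS and CS division.
2. State in the shell that the classification uses Table 7.
3. Add the shift shell that Table 6 note [3] promises: baseline Low/Normal/High against Low/Normal/High at Day 8, at Day 15/Early Termination and at the worst post-baseline value, by arm, for systolic pressure, diastolic pressure and pulse. Because a child can be low at one visit and high at another, show the worst value separately for each direction. Present it descriptively.

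The cost is some SAP wording, one revised shell and one new shell. It needs no new data, visits or subjects. The downside is a few more table pages and smaller cell counts.

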9.7. Physical Examination

Post-baseline physical examinations (comprehensive) will be performed at the Final Visit (Visit 4).

Descriptive statistics (frequency and percentage) will be used to summarize physical examination results by body system, treatment group and visit. In addition, the number of subjects with values of potential clinical significance determined by the investigator will be tabulated.

All physical examination data will be listed by treatment and subject.

9.8. Focused ENT/Eye examination

Post-baseline focused ENT/Eye examinations will be performed at Visits 3 and 4.

Descriptive statistics (frequency and percentage) will be used to summarize ENT/Eye examination results by treatment group and visit. In addition, the number of subjects with values of potential clinical significance determined by the investigator will be tabulated.

The focused ENT exam reviews the following 9 symptoms: Nasal irritation, Epistaxis, Mucosal Edema, Nasal Discharge, Mucosal Erythema, Crusting of Mucosa, Throat Irritation, Candidiasis, Post Nasal Drip. A severity grade of “None” is collected on the CRF and considered as a normal value; more severe grades are considered as abnormal value.

For eye examination, results of both left and right eye are considered. The overall evaluation for each subject is determined by the more severe result from either one of the eyes.

All ENT/Eye examination data will be listed by treatment and subject.

9.9. Study Termination Status

A subject may voluntarily discontinue study participation at any time after giving informed consent and before the completion of the last visit of the study. The Investigator may also discontinue the subject's study participation at any time at his/her discretion and for any reason.

The reasons for subject withdrawal will be recorded and may include, but are not limited to:

1. Withdrawal of consent by the subject to continue in the study.
2. Development of a serious or intolerable AE that necessitates discontinuation at the discretion of the Investigator (AE section of the case report form/electronic case report form [CRF/eCRF] must be completed; includes serious adverse event [SAE], death).
3. At the discretion of the Investigator, when he/she believes continued participation is not in the best interest of the subject.
4. At the discretion of the Investigator, when the subject does not adhere to the study procedures.
5. A protocol deviation that, in the opinion of the Sponsor and the Investigator, warrants discontinuation from the study.

On leaving the study, either at the scheduled end of treatment and subsequent follow-up, or following early withdrawal from the study, or at such time when the patient is considered to be lost to follow-up, the date and reason for leaving the study will be recorded.

If there are multiple reasons for early withdrawal/discontinuation, the worst-case scenario should be chosen. Early discontinuation data will be listed by treatment and subject. Early discontinuations due to Inclusion/Exclusion (I/E) criteria violation, in SAS subjects, will be summarized by treatment and I/E criteria.

10. CHANGES IN ANALYSES FROM THE PROTOCOL

None.

Subjects	Number (%) of subjects		
	Placebo NS (N=xxx)	GSP 301 NS (N=xxx)	Total (N=xxx)
Total screened			xxx
Screen failures			xxx
Pre-run-in Period			xxx
Run-in period			xxx
Randomization failures			xxx
Randomized	xxx	xxx	xxx
Terminated early	xxx (xx.x)	xxx (xx.x)	xxx (xx.x)
Completed study	xxx (xx.x)	xxx (xx.x)	xxx (xx.x)
Early termination reason			
Withdrawal by subject	xxx (xx.x)	xxx (xx.x)	xxx (xx.x)
Investigator / Sponsor Decision	xxx (xx.x)	xxx (xx.x)	xxx (xx.x)
Death	xxx (xx.x)	xxx (xx.x)	xxx (xx.x)
Randomization Failure	xxx (xx.x)	xxx (xx.x)	xxx (xx.x)
Lost to follow up	xxx (xx.x)	xxx (xx.x)	xxx (xx.x)
Non-compliance with Study Procedures	xxx (xx.x)	xxx (xx.x)	xxx (xx.x)
Screen Failure	xxx (xx.x)	xxx (xx.x)	xxx (xx.x)
Adverse event	xxx (xx.x)	xxx (xx.x)	xxx (xx.x)
Protocol deviation	xxx (xx.x)	xxx (xx.x)	xxx (xx.x)
Pregnancy	xxx (xx.x)	xxx (xx.x)	xxx (xx.x)
Others	xxx (xx.x)	xxx (xx.x)	xxx (xx.x)

Source: Listing 16.2.1.1, 16.2.1.2

N = Total number of randomized subjects in each treatment group. Percentages are based on N.

Program: xxxx.sas Executed: DDMMYY YYYY HH:MM

Page X of Y

Programming Note:

(1) Percentages for all categories should be based on the number of randomized subjects.

(2) If the column width is not wide enough for the text, do NOT break/truncate the word. Wrap the text around and align with the first text/sentence (i.e. When wrapping, do not allow words to split and indent under the above first letter). This apply to ALL tables/Listings.

Table 14.1.2.1 Summary of Protocol Deviations during Pre-run-in Period (All Enrolled Subjects)

	Number (%) of subjects	
	Total (N=xxx)	
Number of subjects with at least 1 protocol deviation	xxx (xx.x)	
Total deviations	xxx	
Exclusion criteria	xxx (xx.x)	
Inclusion criteria	xxx (xx.x)	
Informed consent	xxx (xx.x)	

Source: Listing 16.2.2.1

N=Number of subjects screened; percentages are based on N.

The same subject may have had more than 1 protocol deviation.

Program: xxxx.sas Executed: DDMMYYYY HH:MM

Page X of Y

Programming Notes: Need to verify protocol deviations (from the CRF) occurring during this period - before receiving Run-in treatment

Table 14.1.2.2 Summary of Protocol Deviations during Placebo Run-In Period (Run-in Set)

	Number (%) of subjects
	Total (N=xxx)
Number of subjects with at least 1 protocol deviation	xxx (xx.x)
Total deviations	xxx
Exclusion criteria	xxx (xx.x)
Inclusion criteria	xxx (xx.x)
Informed consent	xxx (xx.x)
Did not Satisfy Inclusion/Exclusion That May Have Significant Influence on Efficacy (Major PD) [a]	xxx (xx.x)
Other deviations	xxx (xx.x)

Source: Listing 16.2.2.1

Run-in Set: Subjects enrolled in placebo run-in period (between the subjects signing informed consent and administration of the first dose of the randomized study medication) and will be used for presenting run-in period AEs, concomitant medication and protocol deviations.

N=Number of subjects in the run-in population; percentages are based on N.

The same subject may have had more than 1 protocol deviation.

[a] Major PDs occurring in the Run-in period, that contribute to the PP exclusions

Program: xxxx.sas Executed: DDMMYY YYYY HH:MM

Programming Notes: Need to verify protocol deviations (from the CRF) occurring during this period - run-in period.

Table 14.1.2.3 Summary of Protocol Deviations during Randomized Treatment Period (Safety Analysis Set)

	Number (%) of subjects		
	Placebo NS (N=xxx)	GSP 301 NS (N=xxx)	Total (N=xxx)
Number of subjects with at least 1 protocol deviation	xxx (xx.x)	xxx (xx.x)	xxx (xx.x)
Total deviations	xxx	xxx	xxx
Concomitant medication	xxx (xx.x)	xxx (xx.x)	xxx (xx.x)
Exclusion criteria	xxx (xx.x)	xxx (xx.x)	xxx (xx.x)
Inclusion criteria	xxx (xx.x)	xxx (xx.x)	xxx (xx.x)
Informed consent	xxx (xx.x)	xxx (xx.x)	xxx (xx.x)
Study treatment compliance	xxx (xx.x)	xxx (xx.x)	xxx (xx.x)
Study treatment randomization	xxx (xx.x)	xxx (xx.x)	xxx (xx.x)
Investigator record keeping source docs	xxx (xx.x)	xxx (xx.x)	xxx (xx.x)
Study treatment administration/dispense	xxx (xx.x)	xxx (xx.x)	xxx (xx.x)
Visit scheduling	xxx (xx.x)	xxx (xx.x)	xxx (xx.x)
Did not Satisfy Inclusion/Exclusion That May Have Significant Influence on Efficacy	xxx (xx.x)	xxx (xx.x)	xxx (xx.x)
Not Treated with Treatment Assigned at Randomization, but Wrongly Treated in Another Treatment Group	xxx (xx.x)	xxx (xx.x)	xxx (xx.x)
Other Major Deviations	xxx (xx.x)	xxx (xx.x)	xxx (xx.x)

Source: Listing 16.2.2.1

N=Number of subjects in SAS; percentages are based on N.

The same subject may have had more than 1 protocol deviation.

Program: xxxx.sas Executed: DDMMMYYYY HH:MM

Programming Notes:

1. Need to verify protocol deviations (from the CRF) occurring during this period - randomized period.
2. If a category above has no data in any of the columns, do not display. New categories might be added at BDRM review.

Table 14.1.2.4 Summary of Major Protocol Deviations (Safety Analysis Set)

	Number (%) of subjects		
	Placebo NS (N=xxx)	GSP 301 NS (N=xxx)	Total (N=xxx)
Number of subjects with at least 1 protocol deviation	xxx (xx.x)	xxx (xx.x)	xxx (xx.x)
Total deviations	xxx	xxx	xxx
Concomitant medication	xxx (xx.x)	xxx (xx.x)	xxx (xx.x)
Exclusion criteria	xxx (xx.x)	xxx (xx.x)	xxx (xx.x)
Inclusion criteria	xxx (xx.x)	xxx (xx.x)	xxx (xx.x)
Informed consent	xxx (xx.x)	xxx (xx.x)	xxx (xx.x)
Study treatment compliance	xxx (xx.x)	xxx (xx.x)	xxx (xx.x)
Study treatment randomization	xxx (xx.x)	xxx (xx.x)	xxx (xx.x)
Investigator record keeping source docs	xxx (xx.x)	xxx (xx.x)	xxx (xx.x)
Study treatment administration/dispense	xxx (xx.x)	xxx (xx.x)	xxx (xx.x)
Visit scheduling	xxx (xx.x)	xxx (xx.x)	xxx (xx.x)
Did not Satisfy Inclusion/Exclusion That May Have Significant Influence on Efficacy	xxx (xx.x)	xxx (xx.x)	xxx (xx.x)
Not Treated with Treatment Assigned at Randomization, but Wrongly Treated in Another Treatment Group	xxx (xx.x)	xxx (xx.x)	xxx (xx.x)
Other Major Deviations	xxx (xx.x)	xxx (xx.x)	xxx (xx.x)

Source: Listing 16.2.2.1

N=Number of subjects in SAS; percentages are based on N.

The same subject may have had more than 1 major protocol deviation.

Program: xxxx.sas Executed: DDMMYY YYYY HH:MM

Page X of Y

Programming Notes:

1. Need to verify protocol deviations (all "Major" from the BDRM spreadsheet) regardless of the study period for the SAS subjects.
2. If a category above has no data in any of the columns, do not display. New categories might be added at BDRM review.

Table 14.1.3.1 Summary of Analysis Populations

	Placebo NS (N=xxx)	GSP 301 NS (N=xxx)	Number (%) of subjects Total (N=xxx)
Run-in Set			xxx
Randomized	xxx	xxx	xxx
Not treated as randomized	xxx (xx.x)	xxx (xx.x)	xxx (xx.x)
Did not receive any study medication [a] following randomization	xxx (xx.x)	xxx (xx.x)	xxx (xx.x)
Safety analysis set	xxx (xx.x)	xxx (xx.x)	xxx (xx.x)
Full analysis set	xxx (xx.x)	xxx (xx.x)	xxx (xx.x)
Randomized but excluded from FAS	xxx (xx.x)	xxx (xx.x)	xxx (xx.x)
Did not receive at least one dose of study medication	xxx (xx.x)	xxx (xx.x)	xxx (xx.x)
Did not have at least one post-baseline primary efficacy Assessment	xxx (xx.x)	xxx (xx.x)	xxx (xx.x)
Randomized twice in the same study [b]	xxx (xx.x)	xxx (xx.x)	xxx (xx.x)
Per protocol set	xxx (xx.x)	xxx (xx.x)	xxx (xx.x)
Randomized but excluded from PP due to major protocol deviation	xxx (xx.x)	xxx (xx.x)	xxx (xx.x)

Source: Listing 16.2.1.1, 16.2.3.1, 16.2.3.2

N=Number of subjects randomized; percentages are based on N.

Study medication refers to any study drug taken during the treatment phase of the study

[a] Subject who did not receive a study medication is excluded from safety analysis set.

[b] <will insert footnote case by case, this line might not be necessary>.

Table 14.1.4.1 Summary of Demographic Data (Run-in Set)

Demographic characteristic	Statistics	Total (N=xxx)
Age (years)	n (%) Mean (SD) Median Min, Max	xx (xx.x) xx.x (xx.xx) xx.x xx,xx
Age Group (years) n (%)	6 - < 9 9 - <12 Other Total	xxx (xx.x) xxx (xx.x) xxx (xx.x) xxx (xx.x)
Sex n (%)	Male Female Total	xxx (xx.x) xxx (xx.x) xxx (xx.x)
Race n (%)	White African American Asian American Indian or Alaska Native Native Hawaiian or Other Pacific Islander Other Unknown Total	xxx (xx.x) xxx (xx.x) xxx (xx.x) xxx (xx.x) xxx (xx.x) xxx (xx.x) xxx (xx.x) xxx (xx.x)
Ethnicity n (%)	Hispanic or Latino Not Hispanic or Latino Total	xxx (xx.x) xxx (xx.x) xxx (xx.x)

Source: Listing 16.2.4.1

Run-in Set: Subjects enrolled in placebo run-in period (between the subjects signing informed consent and administration of the first dose of the randomized study medication) and will be used for presenting run-in period AEs, concomitant medication and protocol deviations.

For subject with multiple races, the subject will be counted in each race category.

SD = Standard Deviation; Max=maximum; Min=minimum; N= number of subjects in the treatment Run-in Set group; n= number of subjects with data available; percentages are based on N.

Program: xxxx.sas Executed: DDMMYY YYYY HH:MM

Page X of Y

Table 14.1.4.2 Summary of Demographic Data (Safety Analysis Set)

Demographic characteristic	Statistics	Placebo NS (N=xxx)	GSP 301 NS (N=xxx)	Total (N=xxx)
Age (years)	n (%)	xx (xx.x)	xx (xx.x)	xx (xx.x)
	Mean (SD)	xx.x (xx.xx)	xx.x (xx.xx)	xx.x (xx.xx)
	Median	xx.x	xx.x	xx.x
	Min, Max	xx,xx	xx,xx	xx,xx
Age Group (years) n (%)	6 - < 9	xxx (xx.x)	xxx (xx.x)	xxx (xx.x)
	9 - <12	xxx (xx.x)	xxx (xx.x)	xxx (xx.x)
	Other	xxx (xx.x)		
	Total	xxx (xx.x)	xxx (xx.x)	xxx (xx.x)
Sex n (%)	Male	xxx (xx.x)	xxx (xx.x)	xxx (xx.x)
	Female	xxx (xx.x)	xxx (xx.x)	xxx (xx.x)
	Total	xxx (xx.x)	xxx (xx.x)	xxx (xx.x)
Race n (%)	White	xxx (xx.x)	xxx (xx.x)	xxx (xx.x)
	African American	xxx (xx.x)	xxx (xx.x)	xxx (xx.x)
	Asian	xxx (xx.x)	xxx (xx.x)	xxx (xx.x)
	American Indian or Alaska Native	xxx (xx.x)	xxx (xx.x)	xxx (xx.x)
	Native Hawaiian or Other Pacific Islander	xxx (xx.x)	xxx (xx.x)	xxx (xx.x)
	Other	xxx (xx.x)	xxx (xx.x)	xxx (xx.x)
	Unknown	xxx (xx.x)	xxx (xx.x)	xxx (xx.x)
Ethnicity n (%)	Total	xxx (xx.x)	xxx (xx.x)	xxx (xx.x)
	Hispanic or Latino	xxx (xx.x)	xxx (xx.x)	xxx (xx.x)
	Not Hispanic or Latino	xxx (xx.x)	xxx (xx.x)	xxx (xx.x)
Total		xxx (xx.x)	xxx (xx.x)	xxx (xx.x)

Source: Listing 16.2.4.1

For subject with multiple races, the subject will be counted in each race category.

SD = Standard Deviation; Max=maximum; Min=minimum; N= number of subjects in SAS in the treatment group; n= number of subjects with data available; percentages are based on N.

Program: xxxx.sas Executed: DDMMYY YYYY HH:MM

Page X of Y

Table 14.1.4.3 Summary of Demographic Data (Full Analysis Set)
Repeat table 14.1.4.1 for Full Analysis Set.

Table 14.1.4.4 Summary of Demographic Data (Per Protocol Set)
Repeat table 14.1.4.1 for Per Protocol Set.

Table 14.2.1.1 Summary of Average AM and PM rTNSS by Day (Full Analysis Set)

Treatment Group	Day	Average AM and PM rTNSS by Day				Change from Baseline			
		n	Mean (SD)	Median	Min, Max	n	Mean (SD)	Median	Min, Max
Placebo NS (N = xxx)	Baseline	xx	xx.x (xx. x)	xx.x	(xx,xx)	xx	xx.x (xx. x)	xx.x	(xx,xx)
	1	xx	xx.x (xx. x)	xx.x	(xx,xx)				
	2	xx	xx.x (xx. x)	xx.x	(xx,xx)				
	3	xx	xx.x (xx. x)	xx.x	(xx,xx)				
	***	xx	xx.x (xx. x)	xx.x	(xx,xx)				
	14	xx	xx.x (xx. x)	xx.x	(xx,xx)	xx	xx.x (xx. x)	xx.x	(xx,xx)
GSP 301 NS (N = xxx)	Baseline	xx	xx.x (xx. x)	xx.x	(xx,xx)	xx	xx.x (xx. x)	xx.x	(xx,xx)
	1	xx	xx.x (xx. x)	xx.x	(xx,xx)				
	2	xx	xx.x (xx. x)	xx.x	(xx,xx)				
	3	xx	xx.x (xx. x)	xx.x	(xx,xx)				
	***	xx	xx.x (xx. x)	xx.x	(xx,xx)				
	14	xx	xx.x (xx. x)	xx.x	(xx,xx)	xx	xx.x (xx. x)	xx.x	(xx,xx)

Source: Listing 16.2.6.3

Baseline score is derived as the mean of the last 8 consecutive reading scores including the AM assessment on the day of randomization. Day 1 is derived as the average of Day 1 PM and Day 2 AM assessments, and so on for the rest of the treatment.

SD = Standard Deviation; Max=maximum; Min=minimum; N= number of subjects in the FAS treatment group; n= number of subjects with data available

Program: xxxx.sas Executed: DDMMYY YYYY HH:MM

Page X of Y

Table 14.2.1.2 Summary of Repeated Measures Analysis Results of Average AM and PM rTNSS over the 14-day Treatment Period (Full Analysis Set)

Overall 14-day treatment period

Treatment Group Comparison (GSP 301 NS vs. Placebo NS)	n		LS Mean (SE)		Comparison between GSP 301 NS vs. Placebo NS			
	Placebo	GSP 301	Placebo	GSP 301	LS Mean Difference	SE of LS Mean Difference	95% CI	P-value
	NS	NS	NS	NS	xxx.x	xxx.xx	(xxx.x, xxx.x)	x.XXX
GSP 301 NS vs. Placebo NS	xxx	xxx	xxx.x (xx.xx)	xxx.x (xx.xx)	xxx.x	xxx.xx	(xxx.x, xxx.x)	x.XXX

Source: Listing 16.2.6.3

Baseline score is derived as the mean of the last 8 consecutive reading scores including the AM assessment on the day of randomization. Day 1 is derived as the average of Day 1 PM and Day 2 AM assessments and so on for the rest of the treatment period.

n= number of subjects with data available LS = least squares; SE = standard error

Statistical Analysis model: Mixed-effect repeated measures model with change from baseline as the dependent variable, treatment group and site as fixed effects, baseline score as covariate and study day as the within-subject effect.

Program: xxxx.sas Executed: DDMMYY HH:MM

Page X of Y

Programming Notes:

1. *Repeat the analysis for Days 1 to 14, replacing "Overall 14-day treatment period" with "Day 1", "Day 2", as is appropriate*
2. *Based on the results of the independent modeling for interactions, add the following footnotes:*
 - a. *If only treatment*site interaction is significant, footnote: "Site by treatment interaction is included in the model for the Overall 14-day analysis".*
 - b. *If only baseline*treatment interaction is significant, footnote: "Baseline score by treatment interaction is included in the model for the Overall 14-day analysis".*
 - c. *If both interactions are significant, footnote: "Site by treatment and baseline score by treatment interactions are included in the model for the Overall 14-day analysis".*

Table 14.2.1.3 Summary of Average AM and PM rTNSS by Day (Per Protocol Set)

Source: Listing 16.2.6.3

Repeat Table 14.2.1.1 for per protocol set.

Table 14.2.1.4 Summary of Repeated Measures Analysis Results of Average AM and PM rTNSS over the 14-day Treatment Period (Per Protocol Set)

Source: Listing 16.2.6.3

Repeat Table 14.2.1.2 for per protocol set.

Table 14.2.1.5 Subgroup Analyses (Age Group): Summary of Average AM and PM rTNSS by Day (Full Analysis Set)

Age Group 6 - <9

Treatment Group	Day	Average AM and PM rTNSS by Day				Change from Baseline			
		n	Mean (SD)	Median	Min, Max	n	Mean (SD)	Median	Min, Max
Placebo NS (N = xxx)	Baseline	xx	xx.x (xx. x)	xx.x	(xx,xx)				
	1	xx	xx.x (xx. x)	xx.x	(xx,xx)	xx	xx.x (xx. x)	xx.x	(xx,xx)
	2	xx	xx.x (xx. x)	xx.x	(xx,xx)	xx	xx.x (xx. x)	xx.x	(xx,xx)
	3	xx	xx.x (xx. x)	xx.x	(xx,xx)	xx	xx.x (xx. x)	xx.x	(xx,xx)
	...								
	14	xx	xx.x (xx. x)	xx.x	(xx,xx)	xx	xx.x (xx. x)	xx.x	(xx,xx)
GSP 301 NS (N = xxx)	Baseline	xx	xx.x (xx. x)	xx.x	(xx,xx)				
	1	xx	xx.x (xx. x)	xx.x	(xx,xx)	xx	xx.x (xx. x)	xx.x	(xx,xx)
	2	xx	xx.x (xx. x)	xx.x	(xx,xx)	xx	xx.x (xx. x)	xx.x	(xx,xx)
	3	xx	xx.x (xx. x)	xx.x	(xx,xx)	xx	xx.x (xx. x)	xx.x	(xx,xx)
	...								
	14	xx	xx.x (xx. x)	xx.x	(xx,xx)	xx	xx.x (xx. x)	xx.x	(xx,xx)

Source: Listing 16.2.6.3

Baseline score is derived as the mean of the last 8 consecutive reading scores including the AM assessment on the day of randomization. Day 1 is derived as the average of Day 1 PM and Day 2 AM assessments and so on for the rest of the treatment period.

SD = Standard Deviation; Max=maximum; Min=minimum; N= number of subjects in the FAS treatment group; n= number of subjects with data available

Program: xxxx.sas Executed: DDMMYY YYYY HH:MM

Repeat for Age Group 9-<12.

Table 14.2.1.6 Subgroup Analyses (Age Group): Summary of Repeated Measures Analysis Results of Average AM and PM rTNSS over the 14-day Treatment Period (Full Analysis Set)

Age Group: 6-<9

Overall 14-day treatment period

Treatment Group Comparison (GSP 301 NS vs. Placebo NS)	n		LS Mean (SE)		Comparison between GSP 301 NS vs. Placebo NS			
	Placebo NS	GSP 301 NS	Placebo NS	GSP 301 NS	LS Mean Difference	SE of LS Mean Difference	95% CI	P-value
GSP 301 NS vs. Placebo NS	xxx	xxx	xxx.x (xx.xx)	xxx.x (xx.xx)	xxx.x	xxx.xx	(xxx.x, xxx.x)	x.xxx

Source: Listing 16.2.6.3

Baseline score is derived as the mean of the last 8 consecutive reading scores including the AM assessment on the day of randomization. Day 1 is derived as the average of Day 1 PM and Day 2 AM assessments and so on for the rest of the treatment period.

n= number of subjects with data available LS = least squares; SE = standard error

Statistical Analysis model: Mixed-effect repeated measures model with change from baseline as the dependent variable, treatment group and site as fixed effects, baseline score as covariate and study day as the within-subject effect.

Program: xxxx.sas Executed: DDMMYYYY HH:MM

Page X of Y

Programming Notes:

1. Repeat the analysis for Days 1 to 14, replacing "Overall 14-day treatment period" with "Day 1", "Day 2", as is appropriate
2. Based on the results of the independent modeling for interactions, add the following footnotes:
 - a. If only treatment*site interaction is significant, footnote: "Site by treatment interaction is included in the model for the Overall 14-day analysis".
 - b. If only baseline*treatment interaction is significant, footnote: "Baseline score by treatment interaction is included in the model for the Overall 14-day analysis".
 - c. If both interactions are significant, footnote: "Site by treatment and baseline score by treatment interactions are included in the model for the Overall 14-day analysis".
3. Repeat the analysis for Age Group 9-<12.

Table 14.2.1.7 Subgroup Analyses (Sex): Summary of Average AM and PM rTNSS by Day (Full Analysis Set)

Sex: Male

Treatment Group	Day	Average AM and PM rTNSS by Day				Change from Baseline			
		n	Mean (SD)	Median	Min, Max	n	Mean (SD)	Median	Min, Max
Placebo NS (N = xxx)	Baseline	xx	xx.x (xx. x)	xx.x	(xx,xx)				
	1	xx	xx.x (xx. x)	xx.x	(xx,xx)	xx	xx.x (xx. x)	xx.x	(xx,xx)
	2	xx	xx.x (xx. x)	xx.x	(xx,xx)	xx	xx.x (xx. x)	xx.x	(xx,xx)
	3	xx	xx.x (xx. x)	xx.x	(xx,xx)	xx	xx.x (xx. x)	xx.x	(xx,xx)
	...								
	14	xx	xx.x (xx. x)	xx.x	(xx,xx)	xx	xx.x (xx. x)	xx.x	(xx,xx)
GSP 301 NS (N = xxx)	Baseline	xx	xx.x (xx. x)	xx.x	(xx,xx)				
	1	xx	xx.x (xx. x)	xx.x	(xx,xx)	xx	xx.x (xx. x)	xx.x	(xx,xx)
	2	xx	xx.x (xx. x)	xx.x	(xx,xx)	xx	xx.x (xx. x)	xx.x	(xx,xx)
	3	xx	xx.x (xx. x)	xx.x	(xx,xx)	xx	xx.x (xx. x)	xx.x	(xx,xx)
	...								
	14	xx	xx.x (xx. x)	xx.x	(xx,xx)	xx	xx.x (xx. x)	xx.x	(xx,xx)

Source: Listing 16.2.6.3

Baseline score is derived as the mean of the last 8 consecutive reading scores including the AM assessment on the day of randomization. Day 1 is derived as the average of Day 1 PM and Day 2 AM assessments and so on for the rest of the treatment period.

SD = Standard Deviation; Max=maximum; Min=minimum; N= number of subjects in the FAS treatment group; n= number of subjects with data available

Program: xxxx.sas Executed: DDMMYY YYYY HH:MM

Repeat for Sex: Female.

Table 14.2.1.8 Subgroup Analyses (Race): Summary of Average AM and PM rTNSS by Day (Full Analysis Set)

Race: White

Treatment Group	Day	Average AM and PM rTNSS by Day				Change from Baseline			
		n	Mean (SD)	Median	Min, Max	n	Mean (SD)	Median	Min, Max
Placebo NS (N = xxx)	Baseline	xx	xx.x (xx. x)	xx.x	(xx,xx)				
	1	xx	xx.x (xx. x)	xx.x	(xx,xx)	xx	xx.x (xx. x)	xx.x	(xx,xx)
	2	xx	xx.x (xx. x)	xx.x	(xx,xx)	xx	xx.x (xx. x)	xx.x	(xx,xx)
	3	xx	xx.x (xx. x)	xx.x	(xx,xx)	xx	xx.x (xx. x)	xx.x	(xx,xx)
	...								
	14	xx	xx.x (xx. x)	xx.x	(xx,xx)	xx	xx.x (xx. x)	xx.x	(xx,xx)
GSP 301 NS (N = xxx)	Baseline	xx	xx.x (xx. x)	xx.x	(xx,xx)				
	1	xx	xx.x (xx. x)	xx.x	(xx,xx)	xx	xx.x (xx. x)	xx.x	(xx,xx)
